### **Diagnosis and criteria for inclusion and exclusion:**

The following are the inclusion criteria:

1. Willing and able to provide informed consent
2. Male or female patients > 18 years of age on the day of informed consent
3. Have received a confirmed diagnosis of COVID-19 (positive for SARS-CoV-2), as assessed by PCR or point-of-care within 72 hours of first dose on Day 1
4. Have mild to moderate signs or symptoms of COVID-19 with onset within 5 days of first dose on Day 1, at least two of the following symptoms:
  - stuffy or runny nose
  - sore throat
  - shortness of breath
  - cough
  - fatigue
  - myalgia
  - headache
  - chills or shivering
  - feeling hot or feverish
  - nausea
  - vomiting
  - diarrhea
  - anosmia
  - ageusia

5. Outpatient with COVID-19 disease (not requiring oxygen therapy [WHO COVID-19 Clinical Improvement Ordinal Scale, score of 3])
 
6. Patient is aware of the investigational nature of this study and willing to comply with protocol treatments, blood tests, and other evaluations listed in the ICF.

--

The following are the exclusion criteria:

- 1. Females who are pregnant (negative pregnancy test required for all women of child-bearing potential at Screening) or breast-feeding
- 2. Male patients and women of childbearing potential (women who are not surgically sterile or postmenopausal defined as amenorrhea for >12 months) who are not using at least one protocol-specified method of contraception
- 3. Severe COVID-19 disease as defined by the WHO COVID-19 Clinical Improvement Ordinal Scale, scores of 5 (non-invasive ventilation or high-flow oxygen), 6 (intubation and mechanical ventilation), or 7 (ventilation + additional organ support pressors, renal replacement therapy [RRT], extracorporeal membrane oxygenation [ECMO])
- 4. Expected survival less than 72 hours
- 5. Peripheral capillary oxygen saturation (SpO2) <90% while breathing room air
- 6. Treatment with other drugs thought to possibly have activity against SARS-CoV-2 infection like remdesivir, favipiravir, within 7 days prior to enrollment or concurrently
- 7. History of abuse of drugs or alcohol that could interfere with adherence to study requirements as judged by the Investigator
- 8. Use of any other concurrent investigational drugs while participating in the present study

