### 4.2. Exclusion Criteria

Patients will be excluded from the study if they satisfy any of the following criteria unless otherwise stated:

1. Females who are pregnant (negative pregnancy test required for all women of child-bearing potential at Screening) or breast-feeding
2. Male patients and women of childbearing potential (women who are not surgically sterile or postmenopausal defined as amenorrhea for >12 months) who are not using at least one protocol-specified method of contraception

3. Severe COVID-19 disease as defined by the WHO COVID-19 Clinical Improvement Ordinal Scale, scores of 5 (non-invasive ventilation or high-flow oxygen), 6 (intubation and mechanical ventilation), or 7 (ventilation + additional organ support pressors, renal replacement therapy [RRT], extracorporeal membrane oxygenation [ECMO])
4. Expected survival less than 72 hours
5. Peripheral capillary oxygen saturation (SpO2) <90% while breathing room air
6. Treatment with other drugs thought to possibly have activity against SARS-CoV-2 infection like remdesivir, favipiravir, within 7 days prior to enrollment or concurrently
7. History of abuse of drugs or alcohol that could interfere with adherence to study requirements as judged by the Investigator
8. Use of any other concurrent investigational drugs while participating in the present study
9. Patient requires frequent or prolonged use of systemic corticosteroids ( $\geq 20$  mg of prednisone/day or equivalent for  $>4$  weeks) or other immunosuppressive drugs (e.g., for organ transplantation or autoimmune conditions)
10. Known renal disease with an estimated glomerular filtration rate (eGFR) <50 mL/min based on local laboratory results
11. Patients with clinically apparent liver disease, e.g., jaundice, cholestasis, hepatic synthetic impairment, or active hepatitis
12. Alanine transaminase (ALT) or aspartate transaminase (AST)  $>3 \times$  upper limit of normal (ULN) or alkaline phosphatase or bilirubin levels  $> 2 \times$  ULN based on local laboratory results
13. Co-administration of clinical doses of orlistat with dalcetrapib
14. Inability to swallow oral medications or a gastrointestinal disorder with diarrhea (e.g., Crohn's disease) or malabsorption at Screening

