## **7.4. Vital Signs, Physical Examination, and Other Safety Evaluations**

### **7.4.1. Vital Signs**

Pulse oximetry will be measured as a safety assessment, with saturation <90% triggering a telemedicine assessment.

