#### 5.4 Other Safety Parameters

Pulse oximetry and saturation measurements will take place on screening, Days 1, 3, 5, 7, 10, follow-up visit 1 (Day14) and follow-up visit 2 (Day28/EOS).

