### 6.5.4 Other Safety Parameters

Vital signs [pulse oximetry and peripheral oxygen saturation] at each visit will be summarized overall and by treatment group using descriptive statistics (N, mean, median, standard deviation, Q1, Q3, minimum and maximum). Change from Day 1 will also be presented similarly using descriptive statistics since Day 1 corresponds to the date of first dose.

In addition, saturation will be characterized as: [<90%], [91%-95%], [>95%] at each visit overall and by treatment group. Number and proportion of subjects within each category will be provided.

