Table 3.2.10	Summary of treatment emergent serious adverse events (TESAE) related to study treatment by preferred term and system organ class, Safety population
3.3 Laboratory variables	
Table 3.3.1	Summary of hematology, Safety population
Table 3.3.2	Summary of biochemistry, Safety population
3.4 Other safety parameters	

Table 3.4.1	Summary of vital pulse rate (bmp), Safety population
Table 3.4.1	Summary of vital SpO2 (%), Safety population
Table 3.4.2	Summary of vital SpO2 (%) in categories, Safety population

Figures	
Figure 1	Subject Disposition (flow chart)
Figure 2	Cumulative incidence curve for sustained clinical resolution (excluding cough, sense of smell and taste), ITT population
Figure 3	Cumulative incidence curve for sustained clinical resolution (excluding cough, sense of smell and taste), PP population – Sensitivity analysis
Figure 4	Cumulative incidence curve for sustained clinical resolution (excluding cough, sense of smell and taste) with last observation carried forward, ITT population – Sensitivity analysis
Figure 5	Plot of mean change from baseline in log10 viral load (saliva) with 80% CI at each study visit, ITT population
Figure 6	Plot of mean change from baseline in log10 viral load (nasal swab) with 80% CI at each study visit, ITT population
Figure 7	Cumulative incidence curve for sustained clinical resolution, ITT population
Figure 8	Plot of mean change from baseline in COVID-19 total symptom score with 80% CI at each study visit, ITT population
Figure 9	Frequency distribution plot of WHO clinical outcome scale at each study visit, ITT population

Listings	
Listing 1	Subject disposition
Listing 2	Datasets analyzed
Listing 3	Protocol deviations
Listing 4	Demographics
Listing 5	Concomitant medications
Listing 6	Study medication administration
Listing 7	COVID-19 related symptoms and endpoints
Listing 8	WHO clinical outcome scale
Listing 9	Adverse events and serious adverse events
Listing 10	Deaths

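### The SpO2 reporting categories in SAP 6.5.4 are not exhaustive: a reading of 90% has no row in Table 3.4.2

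*SAP*

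**What the plan says.** SAP 6.5.4 plans two summaries of oxygen saturation. The first treats it as a continuous variable at each visit, with the usual descriptive statistics and the change from Day 1. The second groups it: "saturation will be characterized as: [<90%], [91%-95%], [>95%] at each visit overall and by treatment group". For the grouped version the SAP adds: "Number and proportion of subjects within each category will be provided". SAP Section 7 lists the grouped output as Table 3.4.2, "Summary of vital SpO2 (%) in categories, Safety population". The continuous SpO2 summary is listed there as a separate table.

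The protocol uses a saturation cut in two places, both strictly below 90%. Exclusion criterion 5 (Protocol 4.2 and Synopsis) reads "Peripheral capillary oxygen saturation (SpO2) <90% while breathing room air". Protocol 7.4.1 says "Pulse oximetry will be measured as a safety assessment, with saturation <90% triggering a telemedicine assessment".

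**The concern.** The lowest group ends just under 90 and the next begins at 91, so 90 itself belongs nowhere. The saturation criterion does not exclude a patient at 90%. Such a patient can therefore be enrolled and then measured at up to eight scheduled time points (SAP 5.4: screening, Days 1, 3, 5, 7, 10, 14 and 28), yet has no row in the grouped table at any visit where the reading is 90.

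What is at stake is the accuracy of one safety table. SAP 6.5 plans no formal testing of safety parameters, so the descriptive tables carry the comparison between arms. None of the ten listings in SAP Section 7 covers vital signs or SpO2, so no planned listing would show how many patients were left out.

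**Working it through.** There is no planned figure to reproduce. The check is whether the stated categories cover every possible value exactly once.

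**Inputs.** Categories from SAP 6.5.4: A is x < 90, B is 91 ≤ x ≤ 95, C is x > 95. Protocol cut from 4.2 and 7.4.1: x < 90. The documents do not state the recording resolution, so both whole percent (0 to 100) and steps of 0.1 (0.0 to 100.0) were tested.

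**Coverage of the stated and alternative categories.**

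| Category set | Whole-percent values not covered | 0.1% values not covered | Overlap |
|---|---|---|---|
| <90, 91–95, >95 (SAP 6.5.4) | 90 | 90.0 to 90.9 | none |
| <90, 90–95, >95 | none | none | none |
| ≤90, 91–95, >95 | none | 90.1 to 90.9 | none |
| ≤90, >90–95, >95 | none | none | none |

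**Effect on the table.** At a given visit and arm, let n be the number measured, a the number below 90, b the number in 91–95, c the number above 95, and k the number in the gap. Then n = a + b + c + k.

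- The counts shown add up to a + b + c = n − k, so they fall short of n by k.
- The number at or below 95 is a + k + b. The table gives a + b, again short by k.
- The number below 90 is a, with or without the gap.

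**Effect on percentages.** SAP 6.5.4 does not state the denominator.

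- If it is all patients measured, the percentages add up to (n − k)/n. As an illustration, assume that all 52 patients of an arm are measured. With k = 0 the sum is 100%. With k = 1 it is 51/52 = 98.1%, and with k = 2 it is 50/52 = 96.2%.
- If it is only the patients who fall in a category, the percentages add up to 100% and the omission is not visible. The below-90 percentage is then a/(n − k) instead of a/n, which is slightly higher whenever a and k are both above zero.

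The value of k cannot be obtained from the documents.

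**The case against.** The strongest reply is that almost nothing depends on this. The grouped table supplements a continuous summary that keeps every 90% reading in its N, mean, quartiles, minimum and maximum. No endpoint, population or stopping rule uses the groups. Progression to oxygen therapy is captured separately (SAP 4.2 and 6.4.3.7), as are serious events requiring supplemental oxygen (SAP 6.5.2.2). All of this stands, and it keeps the point minor. It does not close the gap, because the continuous summary does not say how many patients were at 90, and its minimum shows a 90 only where nobody in that arm was lower.

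A reader might go further and infer that patients at the trial's safety limit drop out of the safety reporting. The documents do not support that. Both protocol uses of the cut are strictly below 90%, so a reading of 90 meets neither, and every reading that meets the trigger is counted in the lowest row.

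A reader might also infer that the table understates low saturation. That holds only for the count at or below 95%. The below-90 count is right, and under one choice of denominator its percentage would be slightly too high, not too low. Nor is it certain that the percentages will miss 100%: that needs a reading in the gap and a denominator of all patients measured.

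Finally, a less-than-or-equal sign might have been lost when the text was read from PDF. This cannot be fully ruled out. However, a greater-than-or-equal sign survives in SAP 6.3.6, and a strict cut below 90% agrees with the protocol. Even with the lowest group read as ≤90%, values from 90.1 to 90.9 would remain unassigned if decimals are recorded.

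**Conclusion.** The categories are wrong as written, and the consequence is minor. Following the rule literally gives a Table 3.4.2 that omits every reading of 90% (or 90.0 to 90.9 with decimals) at the visit where it occurs. The shortfall, both against the number measured and in the count at or below 95%, equals the number of such readings.

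The error is limited to descriptive safety output. Efficacy analyses, sample size and significance levels are not touched. The conclusion rests on the category limits being as printed. Any practical effect also depends on at least one reading falling in the gap.

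**What to change.** In SAP 6.5.4, change the lower limit of the middle category from 91% to 90%, so that the groups are [<90%], [90%-95%] and [>95%]. Make the same change in the shell and program for Table 3.4.2. The set is exhaustive without overlap at whole-percent and 0.1% resolution, and it keeps the reporting cut aligned with the one already in the protocol. A set built on ≤90% and >90%-95% would also close the gap but would depart from that cut.

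This alters a reporting category only and leaves every clinical rule as it is. The cost is a one-number edit, best made before the table is produced. It would also help to state in the same sentence whether the percentages use all patients measured at the visit as the denominator.

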## 7 SUMMARY TABLES, FIGURES AND LISTINGS

1 Study subject
1.1 Subject disposition

Table 1.1.1	Subject disposition
Table 1.1.1b	Subject disposition, ITT population
Table 1.1.2	Visits done, ITT population
Table 1.1.3	Protocol deviations, ITT population
Table 1.1.4	Datasets analyzed
1.2 Demographic and baseline characteristics	
Table 1.2.1	Summary of demographics, ITT population
Table 1.2.2	Summary of medical and surgical history, ITT population
Table 1.2.3	Summary of additional medical or surgical conditions, ITT population
Table 1.2.4	Summary of COVID-19 diagnosis, ITT population
1.3 Prior and concomitant medication	
Table 1.3.1	Summary of medication at randomization, ITT population
Table 1.3.2	Summary of concomitant medication, ITT population
1.4 Treatment compliance	
Table 1.4.1	Summary of treatment compliance, ITT population

2 Efficacy analysis	
2.1 Primary analysis	
Table 2.1.1	Summary of and statistical analysis for sustained clinical resolution (excluding cough, sense of smell and taste), ITT population
Table 2.1.2	Summary of and statistical analysis for sustained clinical resolution (excluding cough, sense of smell and taste), PP population – Sensitivity analysis
Table 2.1.3	Summary of and statistical analysis for sustained clinical resolution (excluding cough, sense of smell and taste) with last observation carried forward, ITT population – Sensitivity analysis
2.2 Key secondary analysis	
Table 2.2.1	Summary of and statistical analysis for log10 viral load (saliva), ITT population
Table 2.2.2	Summary of and statistical analysis for log10 viral load (nasal swab), ITT population
Table 2.2.3	Summary of and statistical analysis for area under the curve of log10 viral load (saliva), ITT population
Table 2.2.4	Summary of and statistical analysis for area under the curve of log10 viral load (nasal swab), ITT population
Table 2.2.5	Summary of and statistical analysis for sustained clinical resolution of symptoms, ITT population
2.3 Other secondary analysis	
Table 2.3.1	Summary of and statistical analysis for viral clearance (saliva), ITT population
Table 2.3.2	Summary of and statistical analysis for viral clearance (nasal swab), ITT population
Table 2.3.3	Summary of and statistical analysis for complete clinical resolution (excluding cough, sense of smell and taste), ITT population

Table 2.3.4	Summary of and statistical analysis for complete clinical resolution, ITT population
Table 2.3.5	Summary of and statistical analysis for COVID-19 total symptom severity score, ITT population
Table 2.3.6	Summary of and statistical analysis for WHO clinical outcome scale, ITT population
Table 2.3.7	Summary of and statistical analysis for proportion of subjects with hospitalizations, ITT population
Table 2.3.8	Summary of and statistical analysis for proportion of subjects who progress to oxygen therapy, ITT population
Table 2.3.9	Summary of and statistical analysis for duration of hospitalization, ITT population
Table 2.3.10	Summary of and statistical analysis for death, ITT population

3 Safety analysis	
3.1 Treatment exposure	
Table 3.1.1	Summary of treatment exposure, safety population
3.2 Adverse events and serious adverse events	
Table 3.2.1	Overall summary of treatment emergent adverse events (TEAE), Safety population
Table 3.2.2	Summary of treatment emergent adverse events (TEAE) by preferred term and system organ class, Safety population
Table 3.2.3	Overall summary of treatment emergent adverse events (TEAE) related to study treatment, Safety population
Table 3.2.4	Summary of treatment emergent adverse events (TEAE) related to study treatment by preferred term and system organ class, Safety population
Table 3.2.5	Summary of treatment emergent adverse events (TEAE) leading to treatment discontinuation by preferred term and system organ class, Safety population
Table 3.2.6	Summary of severe treatment emergent adverse events (TEAE) by preferred term and system organ class, Safety population
Table 3.2.7	Overall summary of treatment emergent serious adverse events (TESAE), Safety population
Table 3.2.8	Summary of treatment emergent serious adverse events (TESAE) by preferred term and system organ class, Safety population
Table 3.2.9	Overall summary of treatment emergent serious adverse events (TESAE) related to study treatment, Safety population
Table 3.2.10	Summary of treatment emergent serious adverse events (TESAE) related to study treatment by preferred term and system organ class, Safety population
3.3 Laboratory variables	
Table 3.3.1	Summary of hematology, Safety population
Table 3.3.2	Summary of biochemistry, Safety population
3.4 Other safety parameters	

Table 3.4.1	Summary of vital pulse rate (bmp), Safety population
Table 3.4.1	Summary of vital SpO2 (%), Safety population
Table 3.4.2	Summary of vital SpO2 (%) in categories, Safety population

Figures	
Figure 1	Subject Disposition (flow chart)
Figure 2	Cumulative incidence curve for sustained clinical resolution (excluding cough, sense of smell and taste), ITT population
Figure 3	Cumulative incidence curve for sustained clinical resolution (excluding cough, sense of smell and taste), PP population – Sensitivity analysis
Figure 4	Cumulative incidence curve for sustained clinical resolution (excluding cough, sense of smell and taste) with last observation carried forward, ITT population – Sensitivity analysis
Figure 5	Plot of mean change from baseline in log10 viral load (saliva) with 80% CI at each study visit, ITT population
Figure 6	Plot of mean change from baseline in log10 viral load (nasal swab) with 80% CI at each study visit, ITT population
Figure 7	Cumulative incidence curve for sustained clinical resolution, ITT population
Figure 8	Plot of mean change from baseline in COVID-19 total symptom score with 80% CI at each study visit, ITT population
Figure 9	Frequency distribution plot of WHO clinical outcome scale at each study visit, ITT population

Listings	
Listing 1	Subject disposition
Listing 2	Datasets analyzed
Listing 3	Protocol deviations
Listing 4	Demographics
Listing 5	Concomitant medications
Listing 6	Study medication administration
Listing 7	COVID-19 related symptoms and endpoints
Listing 8	WHO clinical outcome scale
Listing 9	Adverse events and serious adverse events
Listing 10	Deaths

## 9 APPENDICES

### APPENDIX 1

Algorithm used to classify sustained clinical resolution:

For each subject, all ePRO records will be sorted by the date/time. For each assessment, we characterize the record as clinically resolved (i.e., score of 0 for taste and smell and all other symptoms, a score of 0 or 1) or not.

From Day1 to Day10 (or last ePRO assessment before Day14)

- a) If resolved at Day 10 (or last ePRO assessment), identify first date when resolution occurred with no relapse. This is the tentative date of resolution to be confirmed at Day 14 and Day 28.
- b) If not resolved at Day 10 (or last ePRO assessment), re-assess at Day 14.

At Day14:

- c) If resolved for the first time at Day 14 (i.e. was not resolved at Day 10 or before), use date of Day 14 as the tentative date of resolution to be confirmed at Day 28.
- d) If still resolved at Day 14 (i.e. was already resolved at Day10 or before), use date of resolution identified in step a). This is the tentative date of resolution to be confirmed at Day 28.
- e) If not resolved at Day 14, re-assess at Day28.

At Day28:

- f) If resolved for the first time at Day 28 (i.e., was not resolved at Day 14), subject will be classified as resolved within 28 days and date of resolution will be the date of Day 28.
- g) If still resolved at Day 28 (i.e. was already resolved at Day 14), subject will be classified as resolved within 28 days and date of resolution will be the date of resolution identified in step c) or d).
- h) If not resolved at Day 28, subject will be classified as not resolved within 28 days and the date of censoring will be the date of Day 28.

It should also be noted that subjects who do not have an assessment at Day 28 will be classified as non-resolved REGARDLESS if symptoms were resolved up to their last assessment. Date of censoring will be the date of study discontinuation.

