### **4 EFFICACY ENDPOINTS**

#### **4.1 Primary Efficacy Endpoint**

The primary efficacy endpoint is:

- Time to sustained clinical resolution of symptoms (excluding cough, sense of smell and taste)

Sustained clinical resolution is defined as occurring when no key COVID-19 related symptom (excluding cough, sense of smell and taste) has a score higher than 1 over a 72-hour period (as documented using an electronic patient-reported outcome [ePRO] instrument or in the eCRF). The time to resolution will be taken as the time from randomization until the first day of the last 72-hour period where the patient meets the definition of resolution within 28 days. Patients who do not meet the definition of resolution 28 days after randomization will be considered not resolved.

The classification of sustained clinical resolution of symptoms (excluding cough, sense of smell and taste) follows similar steps as the algorithm presented in Appendix 1.

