#### **6.4.3.4 Change from Baseline in COVID-19 Total Symptom Score**

COVID-19 total symptom score will be summarized by treatment group using descriptive statistics (N, mean, median, standard deviation, minimum, and maximum) for each visit as well as for changes from baseline where an 80% CI will also be presented.

Mean changes from baseline will be analyzed using a repeated measures ANCOVA model including effects of treatment, visit (Day5, Day10, Day14 & Day28/EOS), and treatment-by-visit interaction, as well as baseline value of total symptom score and baseline value of total symptom score-by-visit-interaction. An unstructured covariance structure will be used to model the within-patient errors and the Kenward-Roger approximation will be used to estimate denominator degrees of freedom. The combined two highest treatment groups will be compared to placebo in addition to the comparison of individual doses at the following study visits (Day5, Day10, Day14 and Day 28/EOS).

Symptom scores were either reported electronically by the subject or by the site through telephone calls. Except for the assessments done at screening reported in the eCRF, no visit identifiers were attached to these evaluations, only the date of the assessment. Therefore, similar to viral load, the day of assessment of the symptom scores will be classified into visit identifiers as per the algorithm presented in Appendix 2. This will ensure that Day X for symptom score will correspond to Day X for viral load.

A plot of mean change from baseline in COVID-19 total symptom score with 80% CI at each study visit on the ITT population will be presented (Section 7, Figure 6).

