**APPENDIX 2**

To classify the symptom score and viral load assessments to their appropriate visit identifier, the difference in days between the date of the assessment and the date of the first dose will be calculated, and this difference will be classified according to the reporting windows below. This algorithm will ensure that Day X for symptom score will correspond to Day X for viral load. As per the study protocol, Day 1 corresponds to the date of 1st dose in which all assessments were to be done PRIOR to first dose.

Once the visit identifiers are sorted out, Day 1 will be used to establish a baseline visit. If a subject has no Day 1 assessment but a screening one, then the screening assessment is chosen.

In cases where more than one assessment falls within the same reporting window, the first assessment will be chosen.

Note: For the symptom score, if both ePRO and eCRF assessments were done on the same day, then the ePRO was favored.

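### SAP Appendix 1 names only ePRO records, against the SAP's own endpoint definitions, and gives no resolution date for a patient resolved by Day 10, unscored at Day 14 and resolved at Day 28

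*SAP*

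**What the plan says.** **Source of the scores.** SAP 4.1 defines the primary endpoint on symptom scores "as documented using an electronic patient-reported outcome [ePRO] instrument or in the eCRF", and SAP 4.2 uses the same source wording for the key secondary resolution endpoint. SAP 6.4.3.4 explains why two sources exist: "Symptom scores were either reported electronically by the subject or by the site through telephone calls".

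The resolution date is worked out in Appendix 1. SAP 4.2 sends the key secondary endpoint there. SAP 4.1 says the primary classification "follows similar steps as the algorithm presented in Appendix 1", and SAP 4.2 treats complete resolution similarly. Appendix 1 opens with "For each subject, all ePRO records will be sorted by the date/time". Its Day 1 to Day 10 block then falls back three times (heading, step a, step b) to the last ePRO assessment. The eCRF does not appear. The only rule on combining sources is in Appendix 2, which assigns visit labels: "if both ePRO and eCRF assessments were done on the same day, then the ePRO was favored".

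**Missed visits.** Appendix 1 covers a missed Day 10 (use the last ePRO assessment) and a missed Day 28 (non-resolved, whatever came before). It has no rule for a missed Day 14. At Day 28, step f begins "If resolved for the first time at Day 28 (i.e., was not resolved at Day 14" and step g begins "If still resolved at Day 28 (i.e. was already resolved at Day 14". SAP 6.2.2.2 censors a patient who lacks a required assessment, but does not say whether Day 14 is required or at what date to censor.

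**The concern.** An algorithm for the primary endpoint should give every patient one class and one date before unblinding. Here two programmers working in good faith could differ.

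- **Source.** One would use ePRO records alone, as Appendix 1 is worded. The other would use both sources, as the endpoint definition is worded. Valid telephone scores are either dropped or kept.
- **Day 14.** The uncovered pattern is that of an early resolver, who carries the most information about faster recovery. It can plausibly occur. Protocol Appendix 4 allows visits after Screening/Baseline by telephone or digital media and does not count assessments missed at phone visits as deviations. SAP Appendix 2 labels a score as Day 14 only if it falls 11 to 15 days after first dose, so a contact at 16 to 24 days has no label.

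The total symptom score uses both sources under Appendix 2. On a literal reading, two endpoints from the same questionnaire would rest on different records.

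**Working it through.** No figure in the plan is challenged. The planned 127 events reproduce from the protocol's design (one-sided alpha 0.2, 2:1 allocation, look at 73 events, rho = 2, non-binding futility at HR 1): power 0.800, interim boundary HR 1.453, final alpha 0.1862. This point does not alter them.

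**1. Source, read side by side.** SAP 4.1 and 4.2: ePRO or eCRF. SAP 6.4.3.4: electronic or telephone. Appendix 2: both, ePRO favoured on the same day. Appendix 1: ePRO only. Three places admit eCRF scores, and the one that derives the date does not. Applied literally, a telephone-only Day 28 score is not among the sorted records, so the missing-Day-28 rule makes the patient non-resolved.

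**2. Branch coverage.** Status at Day 10 or last assessment (2 levels) × Day 14 (resolved, not, missing) × Day 28 (resolved, not, missing) = 18 patterns. The 12 with a Day 14 score all reach an outcome. The six without one:

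| By Day 10 | Day 28 | Outcome under Appendix 1 |
|---|---|---|
| Resolved | Missing | Non-resolved (explicit) |
| Not resolved | Missing | Non-resolved (explicit) |
| Resolved | Not resolved | Step h |
| Not resolved | Not resolved | Step h |
| Not resolved | Resolved | Step f, by its first-time wording |
| Resolved | Resolved | **No branch** |

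In the last row step f fails because Day 28 is not the first resolution and no unresolved Day 14 was observed. Step g fails because resolution at Day 14 was not observed either.

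**3. Size of the date gap.** The step a date lies between Day 1 and Day 10. Dating at Day 28 instead adds 28 − 10 = 18 to 28 − 1 = 27 days. Example: a patient randomised the day before first dose and resolved from Day 5. SAP 6.4.1 counts date minus randomisation plus 1, so the step a date gives 5 + 1 = 6 and Day 28 would give 28 + 1 = 29. SAP 6.4.1 also imputes 29 days for censored patients when computing medians, so on that reading this resolver would enter the median exactly as a non-resolver does.

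**4. Illustrations under assumed rates.** The documents give no rate of telephone-only Day 28 scores or of missed Day 14 scores; 5% to 20% is assumed here, and the two mechanisms are kept apart.

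*Telephone-only Day 28 discarded.* Expected events are 156 × 0.8 = 124.8. Power uses the Schoenfeld formula with HR held at 1.4 and a placebo share of 1/3.

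| Share of resolvers affected | Events | Power, one-sided 0.2 | Power, two-sided 0.20 |
|---|---|---|---|
| 0% | 124.8 | 0.82 | 0.69 |
| 5% | 118.6 | 0.81 | 0.67 |
| 10% | 112.3 | 0.80 | 0.66 |
| 20% | 99.8 | 0.77 | 0.62 |

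*Day 14 missed.* Simulation with exponential times, about 75% of placebo resolved by Day 28, HR 1.4, 104 versus 52 patients, upper-tail 0.1 and 1000 runs. Power with none missed is 0.68.

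| Day 14 missed | Step a date kept | Dated Day 28 | Censored (at Day 14) |
|---|---|---|---|
| 5% | 0.66 | 0.65 | 0.64 |
| 10% | 0.66 | 0.64 | 0.63 |
| 20% | 0.67 | 0.63 | 0.58 |

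The simulation error is about √(0.65 × 0.35 / 1000) = 0.015, so small differences should not be over-read. At 20% missed, the active-arm median averages about 12 days with the step a date and about 21 with Day 28.

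**The case against.** The best defence is that the SAP, read whole, already answers the source question. The endpoint definitions admit the eCRF, Appendix 2 ranks the two sources, and the Appendix 1 rule for a missing Day 28 speaks of an assessment without saying ePRO. The primary endpoint only follows similar steps, and Appendix 1 cannot be literal for it anyway, since it requires taste and smell scores that the primary excludes. This stands to the extent that the fault is an internal contradiction, harmful only if Appendix 1 is coded as worded. A reader might infer that the SAP as a whole builds the endpoint from ePRO data alone; sections 4.1 and 4.2 rule that out.

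A reader might also infer that the uncovered patient falls to step f and is dated Day 28. The text does not support this. Step f needs a first resolution at Day 28, and a missing Day 14 score is not an observed unresolved status. The date is undefined, not wrong. Nor is the step a date simply the correct one, since it assumes no relapse between Day 10 and Day 28 that nobody recorded.

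The last-observation-carried-forward analysis in SAP 6.4.4 would recover many telephone-only Day 28 resolvers. It is a sensitivity analysis, however, and fills Day 28 only. Finally, SAP 1 moves the emphasis for proof of concept to viral load, which lowers the stakes without removing the need for one rule.

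**Conclusion.** The point holds as a contradiction and a gap. Appendix 1's source wording conflicts with SAP 4.1, 4.2 and 6.4.3.4. If coded literally, it may turn telephone-scored Day 28 resolvers into non-resolvers and may hide an eCRF-only relapse in Days 1 to 10. One pattern of 18 has three defensible outcomes: the step a date, Day 28, or censoring. Under steps f or g the patient would still be a resolver; the class changes only if SAP 6.2.2.2 is taken to apply to Day 14.

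The size in this trial is unknown. Under the assumed rates, the power effects are small at 5% to 10% and become material mainly at 20% or under the censoring reading. The median is more sensitive than the test. A reader might infer a bias between arms, for instance from tolerability at higher doses. The documents give no telephone or missed-visit rates by arm, and every arm takes 12 tablets a day under blinding, so such bias is possible but not shown. This is a clarification to settle before unblinding, not a reason to doubt the primary analysis as a whole.

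**What to change.** In SAP Appendix 1:

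1. Replace the reference to all ePRO records with *all symptom assessments (ePRO or eCRF; ePRO favoured if both on the same day)*, and each reference to the last ePRO assessment with *last assessment*.
2. Add a pre-specified branch for a missing Day 14. For example: *carry the status and date from step a or b to Day 28; if resolved at Day 28, keep the step a date where there is one*. State that this assumes no unobserved relapse.
3. State in SAP 6.2.2.2 that a missing Day 14 alone does not lead to censoring.

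An ePRO-only repeat of the primary analysis, as a check on mode of collection, is optional. The cost is a few lines of SAP text, plus one table if that option is taken, and no new data. The small downside is that self-reported and site-recorded scores are mixed, which SAP 4.1 already accepts.
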